APPENDIX 6 – DEEP Pivotal Subject Flow Chart (Rev. E)

Statistical Analysis Plan		Page 5 of 22
Sponsor	Study	Version
AtriCure	DEEP Pivotal Study	Version 2.0

1 Introduction

This statistical analysis plan (SAP) describes the planned statistical methods to be used during the reporting and analysis of data collected under the Clinical Study Protocol CP2014-1 DEEP Pivotal Study. This SAP should be read in conjunction with the study clinical study plan (CSP) and case report forms (CRFs). This version of the SAP has been developed with respect to the Clinical Study Protocol CP2014-1 DEEP Pivotal Study Revision H 28Sep2022. Any revisions to the protocol or CRFs that impact the planned analyses may require updates to the SAP.

2 Study Objectives

The primary objective of this study is to evaluate the safety and effectiveness of a dual epicardial and endocardial ablation procedure for patients presenting with Persistent Atrial Fibrillation or Longstanding Persistent Atrial Fibrillation utilizing the AtriCure Bipolar System and AtriClip PRO LAA Exclusion System in an endoscopic or open ablation procedure, followed by an endocardial mapping and ablation procedure utilizing commercially available RF based, ablation catheters.

The effectiveness of the device will be demonstrated by establishing that the device effectively eliminates persistent and long-standing persistent atrial fibrillation, atrial flutter, or atrial tachycardia in a clinically significant proportion of treated patients.

2.1 Study Endpoints

The study has one primary effectiveness endpoint, one primary safety endpoint, eight secondary effectiveness endpoints, eight secondary safety endpoints, and four secondary health economics endpoints.

2.1.1 Primary Effectiveness Endpoint

The primary effectiveness endpoint is freedom from any documented AF, atrial flutter, or atrial tachycardia lasting >30 seconds in duration through the 12-month follow-up visit in the absence of Class I or III AADs (with the exception of previously failed AADs at doses not exceeding those previously failed).

Any arrhythmia that occurs within the blanking period or the AAD Optimization period will not be considered a failure (Visit 5 up to Visit 10). The rhythm status used for evaluation of this endpoint will be derived from regularly scheduled monitoring (i.e. Holter, Zio™-Patch, or 30 second ECG) as well as any symptom driven monitoring that is performed.

The following scenarios shall constitute a failure of the primary effectiveness endpoint:

1. Any documented AF, atrial flutter, or atrial tachycardia lasting >30 seconds duration that occurs at any time beginning at the 6-month visit and through the 12-month visit. These will be

Statistical Analysis Plan		Page 6 of 22
Sponsor	Study	Version
AtriCure	DEEP Pivotal Study	Version 2.0

documented on any Core Lab – ECG form with a time interval of “6 Month Post Endocardial” or “12 Month Post Endocardial”.

2. Any previously failed class I or III AAD administered at a dose higher than baseline and between the 6-month visit date plus one day and the 12-month visit date.
3. Any newly introduced class I or III AAD usage beginning at the 6-month visit date plus one day and through the 12-month visit date.
4. DC cardioversion for AF, atrial flutter, or atrial tachycardia that takes place at any time beginning at the 6-month visit date and ending at the 12-month visit date.
5. Catheter ablation or surgical treatment for AF, atrial flutter, atrial tachycardia that takes place at any time beginning at the 3-month visit date and ending at the 12-month visit date.
6. Two or more repeat catheter ablations within the 2nd blanking period.
7. The use of a non-AtriCure study device for creation of any lesions during the surgical epicardial ablation procedure.

For the purposes of this study, atrioventricular nodal reentrant tachycardia (AVNRT), inappropriate sinus tachycardia, and Wolff–Parkinson–White syndrome (WPW) will not be considered procedure failures.

For this study, AtriCure defines failure of an antiarrhythmic drug (AAD) to include ineffectiveness or intolerance of the AAD.

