 Version: Rev H; 11May2021

Page 19 of 129

Property of AtriCure, Inc. Not to be reproduced without permission of AtriCure, Inc.

CONFIDENTIAL

Study Activity	Visit 1	Visit 2	Visit 3	Phone Visit	Visit 4	Visit 5	Visit 6	Visit 7 Phone Visit	Visit 8	Visit 9	Visit 10	Symptom Driven Monitoring	Visit 11	Visit 12, 13, 14, 15	Phone Visits	Study Exit
	Base-line	Epicardial Procedure	Post-Epicardial Procedure ²³	18 Days (Post Epi)	1 Month follow-up ²³	Endo-cardial Procedure ^{22, 23}	Post Endo-cardial Procedure	7 Day	1 Month	3 Month ²⁰	6 Month	Done between 6-12 month visits	12 Month	Year 2, 3, 4, and 5	18, 30, 42, 54 Months	
Visit Timepoint / Window	Up to 45 days		2-3 days post Epi	+/- 2 Days	30 days +7	91-121 days post Epi	1 day post Endo	7 days post Endo +1	30 days post Endo +7	90 days +14	180 days +/- 30	Symptom or Test	365 days + 30	Year +/- 60 days	Approx. 6 Mo post Annual Visit	Exit
Pulmonary Vein Imaging (CT/CTA/MRI)	X ⁷				X ¹²						X ¹²		X ¹⁸			
LAA Imaging (CTA)														X ¹⁸		
Coronary Anatomy Imaging (CT)	X ⁷															
LAA Exclusion Analysis ³						X (TEE)								X(CTA)		
Lung Function Test	X ^{8,9}															
Transthoracic Echocardiography (TTE)	X ⁷															
Esophagoscopy (EGD)		X ²⁵	X ²⁵													
Inclusion/Exclusion Criteria	X	X ¹¹														
Surgical Procedure/Ablation Procedure Details		X														
LAA Management Details		X														
Transesophageal Echocardiography (TEE)		X ¹⁶				X ¹⁹										
EP Ablation Procedure Details						X										
Adverse Event Assessment		X	X		X	X	X	X	X	X	X		X	X ¹⁷		
Concomitant Arrhythmia Treatment ¹⁴			X		X		X		X	X	X		X	X		
24-Hour Continuous ECG Monitoring/ Arrhythmia Monitoring ¹⁵											X		X	X		
Primary Safety Endpoint					X			X								
Symptom Driven Monitoring											X	X	X			

CONFIDENTIAL

Protocol Number: CP-2014-1
 Protocol Name: DEEP Pivotal
 Version: Rev H; 11May2021

Page 20 of 129

Property of AtriCure, Inc. Not to be reproduced without permission of AtriCure, Inc.

CONFIDENTIAL

Study Activity	Visit 1	Visit 2	Visit 3	Phone Visit	Visit 4	Visit 5	Visit 6	Visit 7 Phone Visit	Visit 8	Visit 9	Visit 10	Symptom Driven Monitoring	Visit 11	Visit 12, 13, 14, 15	Phone Visits	Study Exit
	Baseline	Epicardial Procedure	Post-Epicardial Procedure ²³	18 Days (Post Epi)	1 Month follow-up ²³	Endo-cardial Procedure ^{22, 23}	Post Endo-cardial Procedure	7 Day	1 Month	3 Month ²⁰	6 Month	Done between 6-12 month visits	12 Month	Year 2, 3, 4, and 5	18, 30, 42, 54 Months	

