3.0 STUDY ENDPOINTS

3.1 Primary Effectiveness Endpoint

The primary effectiveness endpoint is freedom from any documented AF, atrial flutter, or atrial tachycardia lasting >30 seconds duration through the 12-month follow-up visit in the absence of Class I or III AADs (with the exception of previously failed AADs at doses not exceeding those previously failed).

Any arrhythmia that occurs within the blanking period or during the “AAD Optimization Period” visit will not be considered a failure (Visit 5 up to Visit 10). The rhythm status used for evaluation of this endpoint shall be derived from regularly scheduled monitoring (i.e., Holter, Zio™ Patch, or 30 second ECG), as well as any symptom driven monitoring that is performed.

The following scenarios shall constitute a failure of the primary effectiveness endpoint:

1. Any documented AF, atrial flutter, or atrial tachycardia lasting >30 seconds duration) that occurs at any time beginning at the 6-month visit and through the 12-month visit.
2. Any previously failed class I or III AAD administered at a dose higher than baseline and between the 6-month visit and the 12-month visit.
3. Any newly introduced class I or III AAD usage beginning at the 6-month visit through the 12-month visit.
4. DC cardioversion for AF, atrial flutter, or atrial tachycardia that takes place at any time beginning at the 6-month visit through the 12-month visit.
5. Catheter ablation or surgical treatment for AF, atrial flutter, atrial tachycardia that takes place at any time beginning at the 3-month visit and ending at the 12-month visit.
6. Two or more repeat catheter ablations within the 2nd blanking period
7. The use of a non-study device for creation of any lesions during the surgical epicardial ablation procedure

For the purposes of this study, atrioventricular nodal reentrant tachycardia (AVNRT), inappropriate sinus tachycardia, and Wolff–Parkinson–White syndrome (WPW) will not be considered procedure failures.

For this study, AtriCure defines failure of an antiarrhythmic drug (AAD) to include ineffectiveness or intolerance of the AAD.

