3.5 Secondary Endpoints – Health Economics

All health economics endpoints are exploratory in nature.

1. Utilization of cardioversion, defined as the number of cardioversion events (visits) that a subject had in the past 12-month period. This endpoint will be measured at the 12-month, 2-, 3-, 4-, and 5-year (Visits 11-15) follow-up visits.
2. Hospital readmissions for AF, atrial flutter, or atrial tachycardia, defined as the number of readmissions in the past 12-month period. This endpoint will be measured at the 12-month, 2-, 3-, 4-, and 5-year (Visits 11-15) follow-up visits.
3. Total length of stay for all hospital readmissions for AF, atrial flutter, or atrial tachycardia, defined as the sum of the length of stay for each such visit within the last 12-month period. This endpoint will be measured at the 12-month, 2, 3, 4, and 5-year (Visits 11-15) follow-up visits.
4. Emergency Room Visits for AF, atrial flutter, or atrial tachycardia, defined as the number of visits in the past 12-month period. This endpoint will be measured at the 12-month, 2-, 3-, 4-, and 5-year (Visits 11-15) follow-up visits.

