11.3 Core Laboratories

ECG Core Laboratory

An independent ECG core laboratory will be utilized for assessment of the following data collected on subjects. All data submitted to the core laboratory will be reviewed and the core laboratory will interpret the reading.

- Visit 10 and Visit 11: ECG collected at follow-up study visits
- Visit 10 and Visit 11: Continuous ECG monitoring recordings (Holter or ZioTM Patch)
- Visit 10 thru Visit 11: Symptom driven monitoring

All ECG monitoring shall be performed in accordance with the core laboratory's recommended protocol which is provided to the sites in the Study Reference Manual.

Imaging Core Laboratory

Left Atrial Appendage: An independent core laboratory will be utilized for assessment of the complete exclusion of the LAA defined by lack of fluid communication (<3 mm residual communication with LAA and < 10mm residual pocket) between the LA and LAA.

Images to be sent by the site include:

- Visit 5: (TEE) Endocardial Procedure Visit
- Visit 11: (CT/CTA/MRI) 12-month post Endocardial Procedure Visit.

Pulmonary Veins: If a subject exhibits symptoms suggestive of pulmonary vein stenosis, the baseline and subsequent CT/MR imaging will be submitted by the site to an independent imaging core laboratory for analysis.

- Images sent to core lab (as applicable) for Visit 4, Visit 10, Visit 11

Consistent with the recommendation from the 2012 HRS/EHRA/ECAS Expert Consensus Statement in Surgical and Catheter Ablation of AF, PV stenosis is categorized as mild < 50%, moderate 50-70% and severe ≥ 70% reduction in the diameter of a PV or PV branch.

Esophagoscopy Core Laboratory

Esophagoscopy (EGD): An independent core laboratory will be utilized for adjudication of any esophageal injuries discovered on the post epicardial procedure EGD. All data submitted to the core laboratory will be reviewed and the core laboratory will provide adjudication. An esophagoscopy at Visit 2 will be performed as a baseline assessment. An esophagoscopy at Visit 3 is to be performed 24 to 72 hours post Procedure. If the esophagoscopy at Visit 3 reveals a new acute esophageal injury, subject reports, images, data and relevant documents will be submitted to a core lab.

REFERENCE LIST

¹

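### SAP 2.1.1 ties arrhythmia failures to two core-lab form labels, a narrower source than the endpoint itself; applied literally, some documented recurrences could be scored as successes.

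*SAP*

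**What the plan says.** SAP 2.1.1, scenario 1, opens with a general rule: a documented AF, flutter or atrial tachycardia episode over 30 seconds is a failure if it is one "that occurs at any time beginning at the 6-month visit and through the 12-month visit". The next sentence names the data source. These episodes will be "documented on any Core Lab – ECG form with a time interval of" 6 months or 12 months post endocardial.

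Protocol 3.1, the synopsis and Protocol 9.2.1 define the same endpoint without a core-lab or form-label condition. Rhythm status comes from scheduled monitoring "as well as any symptom driven monitoring that is performed". SAP 2.1.1 repeats that statement about sources.

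Protocol 11.3 lists what the ECG core laboratory receives:
- "Visit 10 and Visit 11: ECG collected at follow-up study visits"
- "Visit 10 and Visit 11: Continuous ECG monitoring recordings" (Holter or patch)
- "Visit 10 thru Visit 11: Symptom driven monitoring"

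The Schedule of Assessments gives symptom-driven monitoring its own column, headed "Done between 6-12 month visits". Neither document says which interval label its core-lab forms carry.

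SAP 5.6.1.1 scores a subject as a success when no failure was recorded from the 6-month through the 12-month visit.

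**The concern.** The second sentence of scenario 1 is the only instruction in the SAP on where to find arrhythmia failures, and it is narrower than the rule it follows. A programmer who takes it at its word would flag arrhythmias on forms with those two labels, apply scenarios 2 to 7, and leave every other subject a success.

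Two kinds of documented recurrence could then be lost:

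1. A symptom-driven recording that the core lab read but filed under a different interval label. The endpoint explicitly includes these recordings.
2. A recurrence recorded only on an unscheduled-visit, emergency-room, hospital or implanted-device tracing. Protocol 11.3 does not list these for the core lab. Adverse-event reporting is not a dependable second route, because Protocol 10.2 lists AF, flutter and atrial tachycardia among events not reportable on the eCRF (the investigator may still report them) and Protocol 10.5.2 exempts the 10.2 events from SAE reporting.

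The LOCF rule in SAP 5.3 can compound the second loss. A subject in sinus rhythm at month 6, with AF on an outside ECG at month 9 and no 12-month recording, would be carried forward as a success.

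The trial is single-arm against a fixed 60% goal, so no control arm would share a loss of failures. Missed failures raise the observed success rate directly.

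**Working it through.** **Step 1. Which recurrences are exposed.**

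| Recurrence, 6- to 12-month visit | Listed for core lab (Protocol 11.3) | Result if scenario 1 is programmed literally |
|---|---|---|
| Visit 10 or 11 ECG, Holter or patch | Yes | Failure |
| Issued symptom monitor | Yes; form label not stated | Failure only if filed under one of the two labels |
| Outside or device tracing, followed by cardioversion, ablation, surgery, or a new or higher-dose Class I/III drug | No | Failure under scenarios 2 to 5, which have no core-lab condition |
| Outside or device tracing, no such treatment | No | Success, unless also caught above |

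The exposure is therefore the second row, if the label differs, and the fourth row.

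**Step 2. The plan's own figure.** Inputs from Protocol 9.3: goal p0 = 0.60, expected p1 = 0.70, one-sided alpha 0.025, power 80%, N = 182.

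n = [(1.960·√(0.60·0.40) + 0.842·√(0.70·0.30)) / 0.10]² = 181.1, rounded up to 182.

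This reproduces the stated N, but only without the continuity correction that Protocol 9.3 says was used; with it the result is 192. That is a separate matter and does not affect what follows.

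**Step 3. Pass rule.** The smallest success count whose exact binomial upper tail at 0.60 is at most 0.025:
- n = 182: at least 123 successes, true type I error 2.1%.
- n = 220 (the maximum treated): at least 147 successes, true type I error 2.2%.

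The protocol specifies an exact binomial test and the SAP a chi-squared test. Without continuity correction, the chi-squared test gives the same cut-offs at both sizes.

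**Step 4. Effect of missed failures.** No miss rate is given, so it is assumed. Let m be the share of true failures scored as successes, with true success at the goal of 0.60. Observed success is then 0.60 + 0.40·m, and the chance of passing is P(X ≥ cut-off) for a binomial with that probability.

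| m (assumed) | Observed success | P(pass), n=182 | P(pass), n=220 |
|---|---|---|---|
| 0 | 60.0% | 2.1% | 2.2% |
| 2% | 60.8% | 3.5% | 3.8% |
| 5% | 62.0% | 6.9% | 7.9% |
| 10% | 64.0% | 17.7% | 21.2% |

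In subjects, n = 182 at 60% success has 182·0.40 = 72.8 expected failures. A 5% miss is about 3.6 subjects and a 10% miss about 7.3.

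**The case against.** The strongest reply is that the second sentence says where failures will be documented, not that other documentation is disregarded, and that an unrestricted rule comes before it. This stands. A reader might infer that the SAP counts an arrhythmia only when it is on one of those forms; that is how the sentence could be programmed, not what it says.

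A reader might also infer that all locally documented recurrences become successes. The documents do not support this. The scheduled recordings and the issued symptom monitor do reach the core lab (Protocol 7.13, 7.14 and 11.3), so the period between visits is monitored and centrally read. Recurrences that lead to treatment under scenarios 2 to 5 still fail. The core-lab form is not among the documents, and symptom-driven readings may be filed under one of the two labels by design.

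It can be said that emergency-room and device tracings are not named as rhythm sources in the protocol either, so counting them would widen the endpoint. This is arguable, but any documented arrhythmia is the headline definition, and the first feasibility study (Protocol 1.0) counted AF found on pacemaker interrogation as failure.

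The health-economics endpoints ("Hospital readmissions for AF, atrial flutter, or atrial tachycardia, defined as the number of readmissions in the past 12-month period") show that AF admissions are anticipated, but not that any would be missed. At Visit 11 the look-back also covers the blanking and optimization periods.

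Finally, a reader might infer that the label rule can err only towards success. That is true of missed failures, but not established for the rule as a whole. Protocol 7.19 has symptom monitoring start after the last blanking period, whereas 7.13 starts it at Visit 10. A label-based rule could therefore also count an episode that preceded the 6-month visit. Local over-calls are possible too, which is a reason for central reading.

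**Conclusion.** The concern holds in limited form. SAP 2.1.1 adds a form-and-label source that the protocol endpoint lacks. It leaves two questions open: which label symptom-driven readings carry, and whether a recurrence documented only outside the core-lab stream counts. Because no recorded failure means success, following the stated source literally can misclassify a documented recurrence in the primary endpoint.

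The size cannot be determined from the documents. The chances of passing in the working rest on assumed miss shares of 2% to 10%, a true success rate of exactly 60%, and an analysed n of 182 or 220. They show that a handful of missed failures would move the error rate well above 2.5%, not that this will happen. The rule should be settled before analysis, so that the choice cannot depend on results.

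**What to change.** Reword scenario 1 in SAP 2.1.1 as follows:

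- Define the window by recording date, from the 6-month visit date through the 12-month visit date, not by form label.
- Count core-lab readings in that window under any label, including symptom-driven ones.
- Send site, unscheduled, emergency-room, hospital and device tracings from the window to the core lab when available. Where no tracing can be obtained, count the documented arrhythmia.
- Reconcile SAP 2.1.1 with Protocol 3.1 and with the list in Protocol 11.3.

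The cost is SAP wording, matching changes to the protocol text, a data-merge step, and possibly a slightly lower observed success rate.

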Subjects enrolled in this study were followed for 2 years. The primary efficacy endpoint was the absence of atrial fibrillation (AF) at the 12-month follow-up based on a 14-day auto trigger event monitor, i.e., no episodes of AF, atrial flutter, or atrial tachycardia lasting > 30 continuous seconds, while off all Class I and III antiarrhythmic therapy for at least 4 weeks (except amiodarone which must be 12 weeks), prior to assessment. The primary efficacy endpoint was achieved in 68.4% (95% CI 43.4, 87.4) of the 19 subjects with Holter data available. No episodes of atrial fibrillation or atrial flutter were detected on Holter in all 19 subjects at 12-month follow-up. The primary efficacy endpoint was not met in 6 subjects due to atrial tachycardia episodes; in 2 subjects the failure was based on the subjects being in sinus rhythm on AADs and in 4 subjects the failure was based on the subjects being noted to have AF, either on Holter or based on permanent pacemaker interrogation.

Although the sample size was small for a meaningful interpretation and the analysis was intended to be exploratory, the rate of freedom from AF (68.4%) at 12 months is consistent within the range given in the literature for this patient population.

CP2012-1: Staged DEEP Feasibility Study

AtriCure developed a second feasibility clinical study that was based on the earlier DEEP hybrid study. A staged approach was developed by AtriCure where the subject would undergo an epicardial surgical ablation performed by the cardiac surgeon and approximately 1-10 days following this procedure, the electrophysiologist would perform an endocardial ablation. This procedure occurred during the same hospitalization by the surgeon and electrophysiologist. This staged approach was believed to have logistical advantages over a combined, single-session hybrid procedure.

A total of 30 subjects were enrolled in the feasibility study, with 25 subjects treated with the surgical index procedure and 24 received the endocardial ablation procedure. The Thirty (30) Day Safety Data and annual report has been submitted to the FDA. Subjects are in follow-up and primary endpoint effectiveness data has not be evaluated as subjects are currently returning for 12-month follow up evaluations to assess freedom of AF, atrial flutter, or atrial tachycardia lasting > 30 continuous seconds.

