5.1.8 Post Epicardial Surgical Procedure - Antiarrhythmic Medication Therapy

Subjects may be placed on a Class I or III AAD from the time following the surgical ablation procedure through the time of their Endocardial EP Ablation Procedure utilizing institutional practices, understanding that a washout period should be utilized for each medication, as appropriate. Amiodarone may be used immediately following the surgical procedure (up to one (1) day post procedure).

5.2 1st Blanking Period - Epicardial Surgical Ablation Procedure through Endocardial EP Ablation Procedure

Atrial Flutter and Atrial Tachycardia during First Blanking Period

Subjects that are in atrial fibrillation following the surgical procedure are to be treated with medication therapy prior to their EP procedure. Subjects will only be treated with a catheter ablation within the 90 Day blanking period if the subject has a non-manageable atrial tachycardia. At this time, the subject will receive the full Endocardial EP Ablation Procedure. The timing of this procedure will facilitate a new visit window timeline for the subject. **Please contact AtriCure to receive a new visit window timeline.** This will be documented in the eCRF.

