5.3.1 Pre-Endocardial EP Ablation Procedure

Each subject should return between Day 91 – Day 121 to have the Endocardial EP Ablation Procedure performed by an Electrophysiologist.

Pre-Endocardial EP Ablation Procedure Subject Assessment

Pre-procedure data must be collected prior to starting the EP ablation procedure. See **Visit 5** for a detailed description of data to be collected.

Pre-Endocardial EP Ablation Procedure Proton-Pump Inhibitor (PPI) Therapy

It is required that an acid reducing agent be prescribed 7-days prior to the procedure and continued for a minimum of 30-days post procedure.

Patient Review

Review will be conducted with patient regarding AEF warning signs and treatment with review of the patient emergency wallet card and patient educational brochure.

Pre-Endocardial EP Ablation Procedure Antiarrhythmic Medications

If subject was placed on an AAD following the surgical procedure, it is recommended that the AAD should be discontinued for at least five (5) days (or 5 half-lives) prior to performing the EP catheter procedure to allow adequate drug washout (amiodarone should be discontinued 45 days prior to the Endocardial EP Ablation Procedure).

Pre-Endocardial EP Ablation Procedure Antithrombotic Medications

To protect subjects from bleeding or thromboembolic events, investigators may utilize their institutional procedures for anticoagulation/antiplatelet therapy, in recognition of various oral anticoagulants available as well as individual subject factors such as CHADS₂ or CHA₂DS₂VASc score.

Subjects may undergo their Endocardial EP Ablation Procedure on therapeutic levels of their oral anticoagulant (e.g., INR 2.0 - 2.5 for warfarin held for 12-24 hours prior to the procedure or based on institutional SOC) in order to protect against thromboembolic events.

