- dabigatran (Pradaxa) – when necessary utilize aPTT or ECT to assess for anticoagulant activity.
- apixaban (Eliquis) - no need to monitor anticoagulation effect, in cases of suspected non-compliance, or in other unusual circumstances, assessment of the anticoagulant effect of apixaban may be appropriate. The Chromogenic anti-Factor Xa chromogenic assays are preferable to the PT test because they yield more accurate results but may be used in emergency situations when an anti-Factor Xa assay is not available.
- Rivaroxaban (Xarelto) - routine measurement of Rivaroxaban plasma levels or its pharmacodynamics effects is not required or recommended. The Chromogenic anti-

Factor Xa chromogenic assays are preferable to the PT test because they yield more accurate results but, may be used in emergency situations when an anti-Factor Xa assay is not available.

5.3.5 Post EP Procedure (2nd Blanking Period) Antiarrhythmic Medication Therapy – AAD Management and Recommended Guideline

Following the EP ablation procedure, a subject may be continued on an AAD for up to 90 days (which shall be called the Post Endocardial EP ablation procedure blanking period). If the subject is in sinus rhythm at the 3-month post endocardial EP ablation procedure, the subject's AAD therapy will be discontinued. If the atrial arrhythmia returns, the subject may be returned to AAD therapy utilizing an AAD that the subject previously failed at a dose not exceeding those previously failed from baseline. The 3-month period between the blanking period and the 6-month visit will be utilized for AAD medication optimization. An arrhythmia will not be considered an effectiveness failure during this time period. AAD medication must be optimized prior to the 6-month visit, at which time any arrhythmias will be counted towards the effectiveness endpoints. At the 6-month visit, if the subject is in sinus rhythm on a previously failed AAD at a dose not exceeding previously failed, the subject may remain on the AAD.

Re-ablation to treat Atrial Fibrillation, Atrial Tachycardia, and Atrial Flutter following Endocardial EP Catheter Ablation

Subjects that experience atrial fibrillation, atrial tachycardia, or atrial flutter may be treated with a catheter ablation if deemed medically necessary following the Endocardial EP Ablation Procedure.

Second Blanking Period Catheter Ablation

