5.6.1.1 Primary Analysis

The statistical analysis of the primary effectiveness endpoint will consist of a comparison of the proportion of patients who remain a primary effectiveness success at the 12-month visit to a historical control rate that is based on results from the feasibility trials and published literature. The primary effectiveness endpoint will be assessed with the following hypothesis:

$$H_0: p_E \leq 0.60$$

$$H_a: p_E > 0.60$$

where p_E = the proportion of primary effectiveness success. The hypothesis will be evaluated using a one-sided chi-squared test at a one-sided $\alpha=0.025$ level of significance. The objective will be met if the estimated one-sided p-value is < 0.025. The mITT population will be the primary population for this analysis. Missing values will be treated as described in the Missing Values section 5.3 with the primary method being the LOCF method.

The proportion of primary effectiveness successes will be calculated with subjects as the experimental unit (i.e., the subject will be considered a success if no primary effectiveness failure was recorded from the 6-month visit through the 12-month visit). The numerator of the proportion will be the number of subjects who are a primary effectiveness success, and the denominator will be the total number of subjects. The endpoint will be presented with the numerator and denominator, the proportion and its 95% two-sided exact binomial confidence interval, and the one-sided p-value.

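### SAP scenarios 2 and 3 start counting antiarrhythmic drug use the day after the 6-month visit whose rhythm recording is scored, and scenario 3 does not define newly introduced

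*SAP*

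**What the plan says.** The headline endpoint in SAP 2.1.1 is freedom from arrhythmia "in the absence of Class I or III AADs (with the exception of previously failed AADs at doses not exceeding those previously failed". Only previously failed drugs at no higher dose are exempt.

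Scoring runs on a list of failure scenarios. SAP 5.6.1 refers to 2.1.1 for the failure events, and SAP 5.6.1.1 states that "the subject will be considered a success if no primary effectiveness failure was recorded from the 6-month visit through the 12-month visit". Two scenarios concern AADs. Scenario 2 covers a previously failed drug at a higher dose. Scenario 3 reads "Any newly introduced class I or III AAD usage beginning at the 6-month visit date plus one day and through the 12-month visit date". The SAP opens both on the day after the 6-month visit. Scenarios 1 (rhythm) and 4 (cardioversion) open at the 6-month visit itself.

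Protocol 3.1 words scenario 3 as "Any newly introduced class I or III AAD usage beginning at the 6-month visit through the 12-month visit", without the extra day. Neither document defines newly introduced, and neither sets a drug-free interval before the window opens.

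On AAD use before the window, Protocol 5.1.8 says "Subjects may be placed on a Class I or III AAD from the time following the surgical ablation procedure through the time of their" endocardial procedure. Protocol 5.3.5 lets an AAD be continued for up to 90 days after that procedure, without limiting which drug. It provides for stopping "If the subject is in sinus rhythm at the 3-month post endocardial EP ablation procedure", names only a previously failed AAD for a return to therapy, and expects AAD optimization to be finished before the 6-month visit.

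**The concern.** The trial has one arm and a fixed 60% goal, so a rhythm held by a drug outside the exemption would be credited to the procedure with no control arm to reveal it.

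The 6-month visit carries weight. Its continuous recording is one of only two scheduled in the assessment window (Protocol 7.13 and 7.14). Under SAP 5.2, one visit after the second blanking period with non-missing effectiveness data is enough to enter the mITT population, which is the primary one. Under SAP 5.3, LOCF then carries that status to month 12. A 6-month recording made on a never-failed AAD could therefore be the whole basis for a success.

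The documents recognise carry-over elsewhere. The first feasibility study assessed its endpoint "while off all Class I and III antiarrhythmic therapy for at least 4 weeks (except amiodarone which must be 12 weeks), prior to assessment". Protocol 5.3.1 says that "amiodarone should be discontinued 45 days prior to the Endocardial EP Ablation Procedure".

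**Working it through.** **1. How each case is scored.** Newly introduced can mean (A) a drug not previously failed, or (B) a drug first started inside the window. For a never-failed Class I or III AAD:

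| Case | SAP, A | SAP, B | Protocol 3.1, A | Protocol 3.1, B |
|---|---|---|---|---|
| Last dose before the 6-month visit day | no failure | no failure | no failure | no failure |
| Begun earlier, last dose on the visit day | no failure | no failure | failure | no failure |
| Begun earlier, continued past the visit | failure | no failure | failure | no failure |
| Started on the visit day and continued | failure | no failure | failure | failure |
| Started after the visit day | failure | failure | failure | failure |

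Scenario 2 never applies, because the drug is not a previously failed one. In row 2 the SAP records no failure on either reading, although the same day's rhythm is scored. Row 3 depends entirely on the undefined term. Row 4 is missed only if scoring goes by start date.

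**2. Reach of carry-over.** Visit windows are from Protocol 7.12 to 7.14: Visit 9 on days 90 to 104, Visit 10 on days 150 to 210, Visit 11 on days 365 to 395. The feasibility intervals are 4 weeks (28 days) and 12 weeks (84 days, amiodarone).

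- Stopped at Visit 9: the gap to Visit 10 is 150 − 104 = 46 days to 210 − 90 = 120 days. This always exceeds 28 days but can fall short of 84.
- Stopped at Visit 10: the gap to Visit 11 is at least 365 − 210 = 155 days, beyond 84. The 12-month recording is outside both intervals.

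Carry-over therefore mainly concerns the 6-month recording and early symptom-driven monitoring.

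**3. The planning figure.** Inputs from Protocol 9.3: goal p0 = 0.60, expected p1 = 0.70, one-sided alpha 0.025, power 80%.

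n = [(1.960·√(0.60·0.40) + 0.842·√(0.70·0.30)) / 0.10]² = 181.1, so 182. This is the stated N, although the text says a continuity correction was used, which would give 191.0. That is a separate matter and does not affect this point.

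At N=182 the exact test needs at least 123 successes: alpha 0.021, power 0.787. The uncorrected chi-squared test has the same cut-off.

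**4. Sensitivity to misclassification.** The documents give no rate of never-failed AAD use, so the share m of subjects wrongly scored as successes is assumed. P(goal met) is the probability of at least 123 successes among 182 at rate 0.60 + m. Remaining power is the same probability at 0.70 − m, which applies if the planning rate already includes such subjects.

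| m | Subjects of 182 | P(goal met), true rate 60% | Remaining power |
|---|---|---|---|
| 0 | 0 | 0.021 | 0.79 |
| 1% | about 2 | 0.039 | 0.69 |
| 2% | about 4 | 0.069 | 0.58 |
| 3% | about 5 | 0.114 | 0.47 |
| 5% | about 9 | 0.26 | 0.26 |

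At N=220 (at least 147 successes, alpha 0.022), P(goal met) for m = 1%, 2%, 3% and 5% is 0.044, 0.079, 0.135 and 0.312.

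**The case against.** The strongest reply is that a sensible programmer would adopt reading A. The headline exempts only previously failed drugs, scenario 2 covers those, and scenario 3 is then the natural complement. It also speaks of usage, not of starting. Secondary effectiveness endpoint 5 bars any AAD use after the optimization period except previously failed drugs without a dose increase. On this view a never-failed AAD continued past month 6 fails. This stands as the better reading, so a reader who infers that the plan definitely scores such a subject as a success goes too far. The wording still permits reading B, and under it one subject could pass the primary endpoint and fail secondary endpoint 5.

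The treatment text also narrows the route. Protocol 5.3.5 caps use after the endocardial procedure at 90 days and names only previously failed AADs for restart or for staying on treatment at 6 months. Use after surgery runs only to the endocardial procedure, with washout recommended before it. That too stands, but 5.3.5 is a recommended guideline rather than a scoring rule, and a subject who departs from it must still be scored.

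Two figures invite a larger claim. One is that an 84-day interval from day 180 covers 84/185 = 45% of the nominal window (365 − 180 = 185 days). That is a worst case: never-failed amiodarone stopped on the visit day itself. With the 4-week interval it is 28/185 = 15%. The other is that 2 of 19 feasibility subjects failed while in sinus rhythm on AADs. That endpoint required being off all Class I and III drugs, whereas this one exempts previously failed drugs, and the protocol does not say whether those two subjects' drugs were never-failed. It gives no effect size for this trial.

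**Conclusion.** The concern holds in a limited form. Two defects are established from the text:

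- The SAP opens AAD counting one day later than Protocol 3.1 and one day later than its own rhythm scoring. A never-failed AAD taken up to and including the 6-month visit is therefore no failure, while the recording made on it is scored and can be carried forward.
- Newly introduced is undefined in the rule that decides success.

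The documents do not establish a settled loophole for a drug begun earlier and continued, nor general contamination of the 12-month result.

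The number of affected subjects is not given and may be small. The table in step 4 rests on assumed shares and on the planning N of 182, since the mITT size is unknown. It shows only that a handful of subjects matters: at m = 2%, about four subjects, the false-positive risk is 0.069/0.021, or roughly three times the nominal figure. This should be fixed before analysis, but it does not undermine the design.

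**What to change.** 1. Reword scenario 3 in SAP 2.1.1, Protocol 3.1 and the synopsis as any use within the window, whatever the start date, of a Class I or III AAD not documented at baseline as previously failed. This matches the headline endpoint and secondary endpoint 5.
2. Reconcile the extra day in SAP scenarios 2 and 3 with the protocol's start at the 6-month visit. If the day was added so that a last dose on the visit date would not count, say so explicitly.
3. Prespecify one sensitivity analysis that scores as failures subjects whose last dose of a never-failed AAD fell on the 6-month visit day, or before it within the first feasibility study's interval (4 weeks, 12 weeks for amiodarone).

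These are scoring rules and change no treatment instruction. The cost is a wording amendment and one extra analysis. Protocol 7.19 requires antiarrhythmic drugs to be reported on the eCRF but does not mention stop dates, so their availability must be confirmed before item 3 is adopted. The reported success rate may be slightly lower.
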